14.1 Protocol changes and protocol deviations

Once the trial has started, the investigator must adhere to the protocol and will ensure that it is strictly followed. The investigator, or person designated by the investigator, will document and explain any deviation from the approved protocol. The investigator will promptly report all important amendments and deviations related to non-compliance with the following protocol provisions: inclusion and exclusion criteria, randomization procedures, blinding procedures, informed consent procedure, assignment of subject identification numbers, dosing and assessment schedules, reporting and procedures for adverse events and, any other protocol deviations. The report will also include description of actions taken to prevent recurrence of the detected deviations.

The investigator will be responsible for reporting any protocol deviations or protocol amendments to the Local Ethics Review Committee. The Sponsor will be responsible for reporting to the National Regulatory Authority and the WHO Ethics Review Committee.

No deviations from, or changes to, the protocol will be initiated without prior written Ethics Review Committee approval/favourable opinion of an appropriate amendment.

An exception to this will be in situations when it is necessary to eliminate immediate hazards to the subjects or when the change(s) involves only logistical or administrative aspects of the trial. Under these exceptional circumstances, the investigator should report as soon as possible, the implemented deviation or change, the reasons for it, and, if appropriate, the proposed protocol amendment(s) should be submitted to the Ethics Review Committee for review and approval/favourable opinion, and, to the sponsor for agreement.

In the report of the study, protocol deviations will be summarized and grouped into different categories, including:

- those who entered the study even though they did not satisfy the entry criteria.
- those who developed withdrawal criteria during the study but were not withdrawn.
- those who received the wrong vaccine or incorrect dose.
- those who received an excluded concomitant treatment.
- other deviations

Any deviation(s) from the original statistical plan will be described and justified in protocol amendments and/or in the final report, as appropriate.

Using Appendix 4 (Form 1 and Form 2) individual subjects with protocol deviations will be reported and documented.

The sponsor will implement and maintain quality assurance and quality control systems with written SOPs to assure that the trial is conducted and data are generated, recorded, and reported in compliance with the protocol, GCP and the Indian national regulatory requirement(s) requirement for investigational product. This includes the use of independent trial monitors and independent external audits.

14.2 Trial monitoring

Independent clinical trial monitors will be appointed. The monitors will be under the supervision of an experienced Contract Research Organization that will be in charge of ensuring compliance with Good Clinical Practice and Good Laboratory Practice, A trial initiation monitoring visit will be done prior to enrolment of any volunteer at a site and the clinical monitor and investigator will review the protocol, logistics and all trial related procedures. This includes information on the vaccine and aerosol delivery device, procedures for obtaining informed consent, procedures for reporting SAE and procedures for completing the CRFs.

Site monitoring visits will be scheduled by the clinical monitor on a regular basis. During these visits, information recorded in the CRFs will be verified against source documents for accuracy and completion. The clinical monitor will review the informed consent procedures, product accountability and storage, trial documents and trial progress. The clinical monitor will verify that the investigator follows the approved protocol or amendments (if any). S/he will observe trial procedures and will discuss any problems with the investigator.

Monitoring visits will be recorded in the Monitoring Log at the investigator's site, and at the end of the trial a copy of the completed log will be returned to the sponsor.

14.2.1 SAFETY MONITORING

A Data Safety and Monitoring Board (DSMB) will review safety data collected through day 364. See DSMB Terms of Reference

14.3 Consent forms

To allow compliance with GCP principles, the parent/guardian of each infant will be asked for consent regarding direct access to the source documents for monitoring, audit, and inspections. The agreement covering the use of the data or analysis has to be documented in writing, together with the written informed consent for trial participation.

15 Ethical considerations in study design

15.1 Informed consent

See SOP VAD 4/1 and section 8.5, visit 1 and 2 for details

The parents/guardians of potential participants will have the study explained in depth to them and, in addition, will receive a patient information sheet (Study Document 4) and have the opportunity to ask questions or trial staff prior to giving consent. Informed, witnessed, written consent will be recorded on behalf of each participant (by parent/guardian) for trial participation, and other specific aspects of the trial e.g. for day 364 follow up, photography of subjects (Study Document 5).

15.2 Ethical and regulatory approvals

The protocol will be submitted for approval to the Institutional Ethical Committee of KEM Hospital, Pune. In addition, the WHO Ethics Review Committee will review and approve the study.

In addition the protocol will be submitted to the Scientific Advisory Committee of the MOHFW, India. Moreover, the protocol and supporting documentation will be submitted to the Drugs Comptroller General, India in accordance with the Drugs and Cosmetics Act, Schedule Y requirements.

Community leaders will be informed about the social benefits of the study that the data collected in this study will be valuable to the development of a simpler and safer method for measles vaccination and may result in greater numbers of children being protected against measles infection.

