Reactogenicity associated to the aerosol route has been studied using the Mexican traditional device through a controlled approach comparing frequency of adverse effects among children receiving aerosolized measles vaccines with children receiving subcutaneous vaccination. Most frequent symptoms have been fever, rhinitis, cough, exanthema, conjunctivitis, diarrhea and arthralgias. Among 6-year old children, administration of aerosolized measles vaccine has produced statistically significant lower reactogenicity than subcutaneous route. Among 12month-old children, no serious temporally associated events were identified in vaccinated children. Only inflammation of the conjunctivae, (injection or reddening, with or without discharge, and/or teary eyes), was more common among the infants given aerosol (34/59, 57%) compared to subcutaneous vaccine (19/55, 35%) (p = 0.01). Conjunctival hyperemia ("red eyes" and/or "teary eyes") was reported on at least one day of days 1 to 14, with an incidence of 7% - 14% per day of follow-up among the children in the subcutaneous group, and 12% - 19% per day of follow-up in the aerosol group. None of the children required medical treatment. In summary, the aerosol route of measles vaccine administration has been well tolerated and similar to the subcutaneous route. Episodes of conjunctival hyperemia have been more frequent in the aerosol group in 12-month-old children.

In summary, despite extensive clinical experience with measles aerosol immunization in Mexico and studies in South Africa and Thailand, serious adverse events following

immunization have not been reported. However, some experts have noted the need for more extensive evaluation of the safety of this route of administration.

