5.3.2 Safety

To describe the frequency of adverse events following measles aerosol and subcutaneous vaccination.

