6.2.2 Safety

6.2.2.1 Primary outcome

Adverse events up to and including day 91 post-vaccination;

Adverse events include acute clinical reactogenicity, other adverse events, and serious or unexpected adverse events.

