6.3.2.1 Blinding of safety assessment

It will not be possible to guarantee the blinding of assessors of safety outcomes. Parents/guardians of participants will know which vaccination route their child received. To minimize bias there will be no record of intervention allocation on CRFs for follow up visits and parents/guardians will be asked identical structured, non-leading questions.

An independent Data Safety and Monitoring Board (DSMB) will have access to unblinded data for the assessment of serious adverse events.

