8.4.2 Enumeration of potential study participants

The method of enumeration will depend on the study area:

- For Vadu, an initial tentative list of all eligible children aged 6 to 10 months will be obtained from the Demographic Surveillance System, Vadu.
- For the other study areas, the study field worker will obtain a list of all eligible children aged 6 to 10 months from local health workers. For full details of this process, please see SOP VAD 3/1. These lists will be in a non-electronic form initially, but in the course of recruitment, details of potential participants will be recorded electronically.

Field workers will visit the parents/guardians of potential participants 2-4 weeks before the infant is 9 months old (Visit 1, see below).

Parents/guardians will be encouraged to consult peers, community leaders and other parents who are study participants. In addition, advertisements about the trial will be displayed in prominent places like gram panchayat offices, temples, and schools in the village.

Parents attending clinics for the vaccination of their child prior to nine months of age (e.g. DPT vaccination at 4 months), will also be given information about the trial.

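### Protocol 15.2 has community leaders told of a 'safer' method while safety is a primary question, an avoidable risk of expectation bias in parent-reported mild adverse events

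*Supplement*

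**What the plan says.** Section 15.2 of the protocol: "Community leaders will be informed about the social benefits of the study", and what they are to hear is that "the data collected in this study will be valuable to the development of a simpler and safer method for measles vaccination". The aerosol is not named, but it is the only new method under study.

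Section 8.4.1 provides for visits to village leaders in more than 150 villages before recruitment, to ask for their verbal agreement. Section 8.4.2 adds: "Parents/guardians will be encouraged to consult peers, community leaders and other parents who are study participants".

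Safety is a primary objective, worded descriptively (5.3.2): "To describe the frequency of adverse events following measles aerosol and subcutaneous vaccination". The primary safety outcome (6.2.2.1) is "Adverse events up to and including day 91 post-vaccination".

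Section 6.3.2.1 states: "Parents/guardians of participants will know which vaccination route their child received". It also says that blinding of the safety assessors cannot be guaranteed. Against this it sets identical, structured, non-leading questions and follow-up forms that carry no allocation.

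On what is already known, section 4.3.2 ends: "However, some experts have noted the need for more extensive evaluation of the safety of this route of administration".

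**The concern.** Section 15.2 presents greater safety as a benefit of the new method before the trial has measured it. The people who hear this are those whom parents are encouraged to ask for advice, and the same parents later report symptoms knowing the route. A parent who has absorbed the idea that inhalation is the safer route may be less ready to mention a mild or subjective event after it.

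The primary safety summary is the proportion of children with any adverse event (11.1.3), so mild events count in full. The SAP's event list (Table 14.0.1) includes irritability, malaise, anorexia and crying. No margin or test is planned, so the judgement of an acceptable safety profile (5.2) rests on reading the two arms side by side. Differential reporting would distort that reading. Non-leading questions at the visit do not undo an expectation formed beforehand.

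**Working it through.** No figure in the plan decides this point. It is checked by following the message through the documents, then by an illustration on stated assumptions.

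**1. Is 'safer' supported for this age group?** Section 4.3.2 reports conjunctival inflammation in 12-month-olds, just above the trial's 9.00 to 11.99 months:
- aerosol 34/59 = 57.6%;
- injection 19/55 = 34.5%;
- difference 57.6 − 34.5 = 23.1 points, with p = 0.01 in the protocol.

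The same section reports lower reactogenicity with aerosol in 6-year-olds. It summarises the aerosol as well tolerated and similar to injection, with no child needing treatment. For infants the evidence is at best 'similar', with one excess; it is not 'safer'.

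**2. Where do the adverse-event data come from?** Contacts after vaccination day and up to day 91 (8.5, 8.7):
- home visits, at which fieldworkers ask parents: days 3, 7, 10, 17, 21, 28 and 56, which is 7;
- clinic visits with Medical Officer examination: days 14 and 91, which is 2.

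For most children, 7 of 9 contacts rest on the parent's account. Children in the day-28 blood subset also attend clinic on day 28.

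**3. Which events do the safeguards cover?**
- Immediate events: staff observation and vital signs for 30 minutes (8.7.2.1).
- Moderate, severe or unexpected events found at home: Medical Officer examination (8.7).
- Treated events, hospitalizations and deaths: active surveillance (8.7.2).
- Serious and severe events: final classification by the DSMB (8.7.6).

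This leaves mild events at home visits. There the first grading starts from what the parent says, and a mild event may have resolved before the day 14 or day 91 examination.

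**4. How large could it be?** Assumptions, none of them in the documents: equal true event rate p in both arms, and a fraction u of affected children missed in the aerosol arm only. From section 11.2.2, 1,000 per arm.

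Observed aerosol rate pA = p(1 − u). Apparent difference = −p·u. SE = √[pA(1 − pA)/1000 + p(1 − p)/1000]. 95% CI = difference ± 1.96·SE.

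Example with p = 0.50 and u = 0.10: pA = 0.45; difference −5.0 points; SE = √(0.0002475 + 0.00025) = 0.0223; CI −9.4 to −0.6.

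| p | u | Apparent difference, points (95% CI) |
|---|---|---|
| 10% | 10% | −1.0 (−3.6 to 1.6) |
| 10% | 20% | −2.0 (−4.5 to 0.5) |
| 10% | 30% | −3.0 (−5.4 to −0.6) |
| 50% | 5% | −2.5 (−6.9 to 1.9) |
| 50% | 10% | −5.0 (−9.4 to −0.6) |

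These are upper-end illustrations, because u applies per child. A child leaves the any-event numerator only if all of its events go unreported. If each event were missed independently with probability 0.10, a child with two events would be missed with probability 0.10² = 0.01. At p = 50% the shift would then be 0.50 × 0.01 = 0.5 points, not 5.

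**The case against.** The strongest reply is that the text is milder than it first looks and the chain to the data is incomplete.

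- A reader might infer that leaders are told the aerosol is safer. The text does not say so: it speaks of data that help to develop such a method, and makes no comparison of side effects. This stands.
- A reader might infer that leaders will pass the message to parents. Nothing requires it. Consultation is encouraged only, and parents receive risk and benefit information directly at Visits 1 and 2 (8.5.1.1, 8.5.1.2). This stands too, and it weakens the link without removing it.
- A reader might infer that the plan biases the safety comparison towards aerosol. That states a possibility as fact. An unfamiliar inhaled route could equally raise reporting, and the documents give neither size nor direction.
- A reader might infer that parents of children allocated to injection would refuse or drop out. The documents offer no support. Randomization and vaccination take place at the same visit, and the protocol plans best- and worst-case analyses for missing outcomes (11.5.6).
- The safety analysis is a proportion with 95% CI per arm (11.1.3, 12.1.3; SAP 11.8), so no formal test can be invalidated. This is true, but the informal comparison is then all there is, and that is what differential reporting would affect.

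What survives is that the word is not neutral on a primary question, no section asks for neutral wording to leaders, and the safeguards reach mild parent-reported events least.

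**Conclusion.** The point holds as an avoidable risk, not as a demonstrated bias. Section 15.2 attaches 'safer' to the method under study while relative safety is open and the infant data do not establish it. The exposed data are mild, subjective events reported by unblinded parents. The plausible direction favours aerosol, but neither direction nor size can be derived from the documents.

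On the illustrative assumptions, the effect stays within sampling error at a 10% event rate unless under-reporting is near 30%. It could exceed sampling error at a 50% rate with 10% of affected children missed. Serious and severe events are largely protected. The primary immunogenicity outcome is measured by laboratory staff blinded to allocation (6.3.2.2) and is unaffected. This is a cheap improvement in wording and does not threaten the trial's main conclusion.

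**What to change.** In section 15.2, delete 'and safer' and make the message neutral, for example: *Community leaders will be told that the study compares measles vaccine given by inhalation with the usual injection, and that it is not yet known how the two compare in safety and immune response.* The sentence should not promise that the trial will settle the question.

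Use the same message in the village meetings of 8.4.1, and check that the advertisements of 8.4.2 agree with it. The advertisements and parent information sheets are not shown, so no fault in them is assumed.

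The cost is one protocol sentence and a matching change to the meeting message, notified to the ethics committees. Recruitment appeal may be slightly weaker. Data collection, staffing and analysis do not change.

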15.3 Study data confidentiality

On initiation of the study, the investigator will prepare a file containing documents related to the trial. During the study, the investigator will be responsible for updating the file and

regularly adding trial related documents. The investigator will keep the file in a locked cabinet, in a secure area accessible only to the investigator and authorized study staff.

The investigator file and associated source documents will be retained for at least five years after the licensure of the measles aerosol vaccine. Patient identification codes should be kept for at least 15 years after completion of the trial. Written approval from all sponsors must be obtained prior to destroying records.

All study related documents will be kept in locked cabinets at the study site. Filing cabinets with the trial data and the participant information will be locked and accessed only by authorized persons from the sponsor and Regulatory Authorities.

Personal volunteer data will be kept confidential and the privacy of all subjects will be protected in so far as permitted by law. Subject names will appear on the initial documents (CRF) and once enrolled study documents will refer to the subject code (second initial of each name) and assigned study code number Only personnel involved with the study conduct and local and international regulatory agencies may review these records. The investigator will keep in the investigator's files a Subject Identification List and Screening/Enrolment Log (including complete name, age and address).

All proprietary or confidential information communicated to the investigator by or for WHO or communicated to the investigator during the course of and/or as a results of the clinical study is the exclusive property of WHO and/or SIIL, and the investigator will ensure the same shall be kept strictly confidential by him/her or any other person connected with the clinical study and shall not be disclosed, either orally, or in written form, by him/her or such person to any third party without prior written consent of WHO. The investigator shall communicate the results of the clinical study promptly to WHO or its designee.

All rights and interests worldwide in any inventions, know-how, or other intellectual or industrial property rights which arise during the course of and/or as a result of the clinical study which is the subject of the Protocol or which otherwise arise from the information or materials supplied under this Protocol, shall be assigned to, vest in and remain the property of WHO.

15.4 Revaccination of subjects with inadequate immune response

It is ethically responsible to ensure that all children who are shown to have lower than protective antibody titres 91 days post vaccination are revaccinated using standard measles vaccination methods (i.e. subcutaneous measles vaccine as used in this study). To this end, all children found to have PRN titres <120mIU/ml at 91days post vaccination, regardless of vaccination route, will be revaccinated by the subcutaneous route by a team independent to the trial follow up teams. Serological testing will be conducted as soon as is feasible after samples are drawn. Revaccination will occur as soon as possible and a maximum of 6 weeks after the results for each individual is known. Unblinding will only occur to the level of child identification. Study allocation will not be unblinded. Subsequent serological results from children who are revaccinated will not be included in analyses, but they will continue to be monitored for adverse events.

16 Data handling and record keeping

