5.4 Secondary objectives

5.4.1 Immunogenicity

To compare geometric mean antibody titres in infants receiving measles vaccine delivered via a nebulizer/vaccine combination device with subcutaneous measles vaccine;

To compare the immunogenicity of measles vaccine delivered via a nebulizer/vaccine combination device with subcutaneous measles vaccine, according to level of pre-vaccination antibody titre;

To collect blood from subset of children at 28 days and one year after vaccination. These subset will be randomly selected from all children enrolled in the Vadu study area because they will be able to be followed up within the infrastructure of an existing demographic and health surveillance system. For these subsets, the secondary objectives are:

- To compare the immunogenicity of measles vaccine delivered via a nebulizer/vaccine combination device with subcutaneous measles vaccine one year after vaccination;
- To describe the evolution of the antibody response to measles vaccine delivered via a nebulizer/vaccine combination device and subcutaneously over time, at days 0, 28, 91, 364 after vaccination;

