Purpose:

This document describes principles and procedures for statistical aspects of the randomized controlled trial protocol. The document is referred to as the Statistical Analysis Plan (SAP). The contents of the SAP are in accordance with the guidelines of the International Conference on Harmonisation (ICH) of Technical Requirements for Registration of Pharmaceuticals for Human Use and the Consolidated Reporting Standards for Trials extension to non-inferiority trials (1).

3.0 Policy and Scope:

The SAP is applicable to procedures for the statistical analysis of data generated during the MAP trial to be undertaken at Vadu, Maharashtra, India. The planned analyses are outlined in the protocol WHO/MAP/IND/002 August 2008, Section 11.

4.0 General Responsibilities:

The Principal Statistician is responsible for carrying out the statistical analysis of the clinical data according to the protocol and this SAP and to ensure that other responsible staff members perform their duties according to this SAP.

5.0 Materials and Equipments:

Hardware:

- 1. Desktop personal computers with MS Windows Network
- 2. Laptops with MS Windows Network

SOP VEL 1/1:	Statistical Analysis Plan	Page 3 of 61
September 11, 2012		

Software:

1.	Website development	:	XAMPP 1.6.6a (PHP 5.2.5, MySQL 5.0.51a, Apache), Apache friends group, Germany
2.	Statistical Analyses	:	SAS 9.1, SAS Institute Inc., Cary, NC, USA
3.	Audit trail software		Promasys 6.0, PROMASYS BV, Leiden, The Netherlands

6.0 Assessment of Outcomes:

The planned primary and secondary outcomes, and timing of their measurement, are outlined below.

6.11mmunogenicity:

6.1.1 Primary Outcome:

Measles seropositivity at day 91 post vaccination. This is defined as an optical density value (OD) >=0.1 or a plaque reduction neutralisation test (PRNT) result of >=120mIU/ml. Samples with an OD<0.1 at day 91 will be tested by PRNT as well as all samples from the Vadu study site.

6.1.2 Secondary Outcomes:

For all infants:

- Geometric mean ODs, pre-vaccination and at day 91;
- Seroconversion (defined as a change from Enzygnost enzyme-linked immunosorbent assay (ELISA) OD <0.1 to OD >=0.1 (unless PRNT results are available, in which case it is a change from PRNT from <120 to >= 120 mIU/ml) measured in paired samples from day 0 and day 91

For infants from Vadu in 28 and 364 days subsets:

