- Geometric mean titres and ODs at days 0,28,91 and 364 and geometric mean fold changes between these time points to describe evolution of antibody response
- Seropositivity at 364 days in infants with antibody titre >=120 mIU/ml at day 91.
- Seropositivity at days 0, 28, 91 and 364 and changes between these time points

6.2 Safety:

6.2.1 Primary Outcome:

Adverse events (AE) up to and including day 91 post vaccination; AE include acute clinical reactogenicity, other AE, and serious or unexpected AE.

SOP VEL 1/1:	Statistical Analysis Plan	Page 4 of 61
September 11, 2012		

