Table 12.1.4B: Comparison of serological outcomes, by study group and time of sample collection: **ITT cohort**

	AER		SC		Difference	
Time point	n	%	n	%	(AER-SC) 95% CI	
Day 0, seropositive						
Day 91, seropositive						
Day 91, seroconversion						

Legend:

AER – aerosol; SC - subcutaneous

Table 12.1.5A: Comparison of serological outcomes, by study group and time of sample collection for Vadu subset: **Per Protocol cohort**

	AER		SC		Difference	
Time point	n	%	n	%	(AER-SC) 95% CI	
Day 0, seropositive						
Day 28, seropositive						
Day 28, seroconversion						

Legend:

AER – aerosol; SC - subcutaneous

Table 12.1.5B: Comparison of serological outcomes, by study group and time of sample collection for Vadu subset: **ITT cohort**

	AER		SC		Difference		
Time point	n	%	n	%	(AER-SC) 95% CI		
Day 0, seropositive							
Day 28, seropositive							
Day 28, seroconversion							

Legend:

AER – aerosol; SC - subcutaneous

Table 12.1.6A: Comparison of serological outcomes, by study group and time of sample collection for Vadu subset: **Per Protocol cohort**

Time point		AER		SC	Difference	
		%	ó n %		(AER-SC) 95% CI	
Day 0, seropositive						
Day 364, seropositive						
Day 364, seroconversion						

Legend:

AER - aerosol; SC - subcutaneous

SOP VEL 1/1:	Statistical Analysis Plan	Page 27 of 61
September 11, 2012		

Phase II/III	WHO Measles Aerosol Vaccine	Protocol
Clinical Trial	Project	WHO/MAP/IN/002

Table 12.1.6B: Comparison of serological outcomes, by study group and time ofsample collection for Vadu subset: **ITT cohort**

Time point		AER		SC	Difference	
		%	n	%	(AER-SC) 95% CI	
Day 0, seropositive						
Day 364, seropositive						
Day 364, seroconversion						

Legend:

AER – aerosol; SC - subcutaneous

Table 12.1.7: Day 0 and 91 ELISA and PRNT results with Sero-Conversion. (highlighted in yellow)

	Day 91									
				ELISA <().1]	ELISA >:	=0.1	ELISA Not done	
		PRNT	<120	>=120	Not done	<120	>=120	Not done	<120	>=120
	ELISA	<120								
	<0.1	>=120								
y 0)		Not done								
le (Da	ELISA	<120								
Baselin	>=0.1	>=120								
		Not done								
	ELISA	<120								
	Not done	>=120								
		Not done								

Note: Highlighted in grey are the ones, which are "Not Applicable". That is, which are seropositive or unknown at baseline

Phase II/III	WHO Measles Aerosol Vaccine	Protocol
Clinical Trial	Project	WHO/MAP/IN/002

		GMTs		
	AER	SC	Ratio AER/SC	95% CI for
				ratio
Day 0				
OD (all)				
Day 91				
OD (all)				
OD				
(OD >0.1)				
PRNT				

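### Dropping later serology from children revaccinated after day 91 turns the unrestricted one-year comparison into one of day-91 responders

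*Supplement*

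**What the plan says.** Protocol 15.4 sets the trigger: "all children found to have PRN titres <120mIU/ml at 91days post vaccination, regardless of vaccination route, will be revaccinated by the subcutaneous route". On timing it says: "Revaccination will occur as soon as possible and a maximum of 6 weeks after the results for each individual is known". It then removes the later data: "Subsequent serological results from children who are revaccinated will not be included in analyses".

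Protocol 5.4.1 states the one-year objective for the Vadu subset without reference to response: "To compare the immunogenicity of measles vaccine delivered via a nebulizer/vaccine combination device with subcutaneous measles vaccine one year after vaccination".

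SAP 6.1.2 lists two separate one-year seropositivity outcomes. One is conditional by design: "Seropositivity at 364 days in infants with antibody titre >=120 mIU/ml at day 91". The other is not: "Seropositivity at days 0, 28, 91 and 364 and changes between these time points".

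The unconditional outcome feeds the row "Day 364, seropositive" (and a seroconversion row) in Tables 12.1.6A (per protocol) and 12.1.6B (ITT), and also Table 12.2.1.4.1. Table 12.2.1.2 gives GMT ratios at day 364. The SAP does not mention revaccination.

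Every subset child with a day-91 sample will have the result that triggers revaccination, because SAP 6.1.1 states: "Samples with an OD<0.1 at day 91 will be tested by PRNT as well as all samples from the Vadu study site".

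**The concern.** The exclusion depends on an outcome measured after randomisation that may itself be affected by the route of vaccination. If one route produces more day-91 failures, more of its children leave the day-364 tables, and those who remain were selected for having responded. The unconditional outcome then largely collapses into the conditional one, and the ITT label on Table 12.1.6B no longer describes what is in it.

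Unequal failure is foreseeable, though not established. Protocol 4.3.1.2 reports that in four comparative studies below 10 months seroconversion was lower with aerosol, in two of them by more than chance would readily explain. It gives pooled rates of 93.5% v 97.1% at 10-36 months. Enrolment here is at 9.00 to 11.99 months.

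At stake is the answer to a stated secondary objective: how the two routes compare at one year.

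**Working it through.** **The plan's own figure.** SAP 8.1 gives 100 per arm, SD 0.43 on the log10 scale, 5% level (taken as two-sided) and 80% power, and claims that differences under 1.5-fold are detectable. Detectable fold = 10^[(1.960 + 0.842) x 0.43 x sqrt(2/100)] = 10^0.170 = 1.48, so the claim reproduces. At the planning seropositivity of 90%, the rule removes about 10 children per arm. With 90 left, 10^[2.802 x 0.43 x sqrt(2/90)] = 10^0.180 = 1.51, and power for 1.5-fold falls from 82.5% to 78.4%, before any one-year loss to follow-up.

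**Effect on the comparison.** Let a and s be the day-91 responder proportions (aerosol, subcutaneous). The documents do not give these for this trial, so they are assumed over a range. Two failure patterns bracket the answer.

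*All-or-nothing failure, equal persistence r among responders.*
- All children, failures counted as not seropositive: difference = r(a - s).
- Responders only: difference = r - r = 0.
- Example at r = 0.95: 0.95 x 93.5 - 0.95 x 97.1 = 88.8 - 92.2 = -3.4 points. At r = 1 it is -3.6.

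*General titre shift.* Log10 titre at day 91 is normal with SD 0.43, centred so that a proportion a or s lies above log10(120). Day 364 has correlation 0.8 with day 91 and a mean decline of 0.1 (both assumed). All children here means had nobody been revaccinated. Results are by simulation, 2 million per arm.

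| Day-91 responders, aerosol / SC | Removed per 100 | All-or-nothing: all children (r = 0.95 to 1) | All-or-nothing: responders only | Shift: all children | Shift: responders only | Shift: GMT ratio, all then responders |
|---|---|---|---|---|---|---|
| 90 / 90% | 10 / 10 | 0 | 0 | 0 | 0 | 1.00, 1.00 |
| 93.5 / 97.1% | 6.5 / 2.9 | -3.4 to -3.6 | 0 | -5.2 | -3.0 | 0.69, 0.72 |
| 85 / 90% | 15 / 10 | -4.75 to -5.0 | 0 | -6.4 | -3.2 | 0.78, 0.83 |
| 85 / 95% | 15 / 5 | -9.5 to -10.0 | 0 | -13.2 | -6.9 | 0.55, 0.63 |

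Differences are in percentage points of day-364 seropositivity, aerosol minus subcutaneous. Under the shift, 3.0/5.2 = 58%, 3.2/6.4 = 50% and 6.9/13.2 = 52% of the difference survives; the GMT ratio moves less.

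**Adding the excluded results back does not help.** Titres after an injected dose reflect that dose. If all revaccinated children were seropositive at day 364, the all-or-nothing difference would be 0.0 to +0.5 points in the rows above.

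**Do the missing-data rules cover it?** SAP 11.6 treats missing immunogenicity results as missing at random and also plans best- and worst-case runs. Removal here depends on the day-91 titre, so a missing-at-random analysis would have to condition on that titre, and the day-364 tables do not. Neither document says whether results excluded under 15.4 count as missing. If they do, the best case in protocol 11.5.6 would class known day-91 failures as seropositive.

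**The case against.** The case against is substantial.

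- A reader might infer that the plan conceals an aerosol deficit, or that it returns near-equality whatever the failure rates are. The documents support neither. The primary endpoint and the 5% margin sit at day 91, before revaccination and with non-responders included. Table 12.2.1.2 prints day-91 results by arm for the 364-day subset itself, and Table 12.2.1.4.1 sets day 91 beside day 364. Near-equality follows only from all-or-nothing failure with equal persistence.
- The sample size assumes 90% seropositivity in both arms, which gives no bias. Protocol 4.3.1.2 also concludes that aerosol appears at least as immunogenic from 10 months of age.
- The protocol's own one-year seropositivity outcome is conditional on day-91 response, and 15.4 fits it.
- Day 364 is secondary, has no margin and is imprecise. At 93.5% v 97.1% with r = 0.95, the all-children difference of -3.4 has a 95% CI of -12.0 to 5.0.
- If excluded results are treated as missing, the worst-case run already counts revaccinated children as seronegative.
- Revaccination is triggered by PRNT alone, whereas seropositivity is OD at least 0.1 or PRNT at least 120. A Vadu child with OD at least 0.1 and PRNT below 120 is a primary success who is nonetheless to be revaccinated. Calling every revaccinated child a failure would relabel such children.

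All of this limits the size and reach of the point, and the last item must be settled in any repair. What stands is that the objective, the second SAP outcome and the ITT table are unrestricted while the exclusion makes them essentially responder-only. The worst-case run would resolve this only if the plan said that it applies. The word essentially is deliberate: children not actually revaccinated, or with no day-91 result, can remain, and Table 12.2.1.3 keeps a day-91 row below 120.

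**Conclusion.** The concern holds in a limited form. Followed as written, 15.4 conflicts with the unrestricted one-year objective and with Tables 12.1.6A/B, 12.2.1.2 and 12.2.1.4.1. Any difference between arms at day 364 that arises from different day-91 failure is removed if failure is all-or-nothing with equal persistence, and is roughly halved for seropositivity under a general titre shift. At the pooled rates the protocol quotes for a neighbouring age group, that means about -3.5 points becoming 0, or -5.2 becoming -3.0. These sizes rest on assumed day-91 rates, persistence, correlation and decline. If the arms fail equally, there is no bias. The primary non-inferiority conclusion is not affected.

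**What to change.** Amend the SAP and reconcile it with protocol 15.4 before the day-364 analysis:

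1. State the day-364 estimand. In Tables 12.1.6A/B and 12.2.1.4.1 keep every subset child in the denominator and count those revaccinated for a day-91 PRNT below 120 as not seropositive (or not seroconverted) from the allocated vaccine.
2. State how children with OD at least 0.1 but PRNT below 120 at day 91 are classed in those tables.
3. Label Table 12.2.1.3 and the day-364 GMTs in Table 12.2.1.2 as persistence among responders. Carry the day-91 titre forward for GMTs only as a sensitivity analysis, since it ignores waning.
4. Report the number revaccinated by arm, and say whether results excluded under 15.4 enter the best- and worst-case runs.

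The cost is one derived flag and SAP wording, with no extra samples or visits. Day-91 PRNT is planned for all Vadu samples, so the trigger can be derived. Actual revaccination is done by a separate team, so it should be confirmed that its records reach the trial database.
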